2.2. Study Endpoints

2.2.1. Primary Endpoint

- Safety and tolerability will be assessed by monitoring frequency, duration, and severity of AEs and DLTs; through physical examinations; by evaluating changes in vital signs and electrocardiograms (ECGs); and through clinical laboratory blood and urine sample evaluations.
- Part 4 only: ORR, defined as the proportion of subjects who achieve complete remission (CR) or complete remission with incomplete hematologic recovery (CRi).

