- ⁱ Bone marrow biopsy and/or aspirates performed as clinically indicated or at Cycle 1 Day 15 (+ 2 weeks, depending upon chemotherapy recovery), Day 15 (+ 2 weeks) of any cycle where I-DAC is administered, and every other month as clinically indicated, or upon circulating blood cell recovery to assess antileukemic activity (cytogenetic testing is not required if CR is not presented). Note: For subjects who have a significant blast count reduction (as determined by the investigator) but have not completely cleared circulating blasts, the bone marrow during Cycle 2 is still strongly encouraged to be performed to assess the impact of treatment on the bone marrow blast content. See Section 7.6 for additional details.
- ^j If a biopsy is not possible or contraindicated, or if the tissue requirement cannot be satisfied, then this requirement may be waived with approval from the medical monitor. Subjects with a history of allogenic hematopoietic stem cell transplantation should have tissue collected and analyzed locally for the purposes of determining disease status (where applicable); however, their sample does not need to be processed for sequencing due to chimeric potential.
- ^k Immunophenotyping appropriate to AML will be conducted by flow cytometry at screening and when confirming CR.

CONFIDENTIAL

CONFIDENTIAL

Table 10: Laboratory Assessments for I-DAC Combination Cohorts

Visit Day Evaluation/Window	Section	Screening	Cycle 1			Subsequent Cycles ^a		EOT	Safety Follow-Up
		Day -28 to Day -1	D1	D5 ± 1 Day	D15 ± 1 Day	D1	D11 ± 4 Days	+ 3 Days	EOT + 30-35 Days
Overnight fast before assessments	Table 11			X	X				
Comprehensive blood chemistries	Table 21	X ^b	X ^b	X	X	X	X	X	X
Hematology with differential	Table 21	X ^b	X ^b	X	X	X	X	X	X
LFT panel ^c	Table 21	X ^b	X ^b	X	X	X	X	X	X
Coagulation panel ^c	Table 21	X ^b	X ^b		X	X		X	X
Urinalysis	Table 21	X				X ^d		X	X
Lipid panel	Table 21	X				X ^d			
Hepatitis screening	Table 21	X							
Serum pregnancy test	7.5.5.2	X	X ^e						X
PK – plasma ^f	7.8.1			X	X				

^a The Cycle 1 laboratory assessment schedule, with the exception of the overnight fast and PK sample collection, should be followed whenever I-DAC is administered during a cycle for reinduction or consolidation. Urinalysis and lipid panels should also be collected on Day 1 of cycles where I-DAC reinduction or consolidation treatment aligns with a cycle where these are scheduled (eg, Cycle 4).

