7.6. Efficacy Assessments

[figure not shown]
[figure not shown]
The following disease response criteria will be used for each of the malignancies included in this study:

- Acute myeloid leukemia: International Working Group Response Criteria for Acute Myeloid Leukemia ([Cheson et al 2003](#); [Appendix D](#))

[figure not shown]

Treatment cycles may be delayed; therefore, disease response assessments may be delayed as well to synchronize with treatment cycles. A disease assessment may be performed as an unscheduled procedure if clinically indicated. For subjects who discontinue treatment for reasons other than disease progression, every effort should be made to continue monitoring their disease status until start of new anticancer therapy, documented disease progression, death, or the end of the study, whichever occurs first.

[figure not shown]
CONFIDENTIAL

CONFIDENTIAL

**7.6.3. AML, [REDACTED]
[REDACTED] Bone Marrow Examination**

Bone marrow examination (aspirate and biopsy) is required at screening for subjects with diseases that are typically monitored through bone marrow examination, including AML, [REDACTED] [REDACTED] (bone marrow examination may be omitted with approval of the medical monitor).

In the combination cohorts (Parts [REDACTED] 4), if disease status requires assessment with bone marrow aspirate or biopsy, subjects with AML, [REDACTED] [REDACTED] should have a bone marrow aspirate and/or biopsy performed after 1 cycle of therapy (or earlier if clinically indicated), Month 2, and then approximately every 2 months thereafter. Specific requirements for bone marrow examination of each combination cohort are included in the footnotes of each respective table (Section 6). Subjects without circulating blasts at the screening hematology assessment may use a historical biopsy obtained within 60 days before Cycle 1 Day 1 (Day 1), and all data and reports are available for investigator's review.

Samples of bone marrow biopsy and aspirate will be set to Incyte or its designee for additional immune and molecular profiling.

CONFIDENTIAL

CONFIDENTIAL

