Data from the pathology report result from the bone marrow examination will be captured in the eCRF. All bone marrow examinations should include a unilateral aspiration and biopsy with FISH and cytogenetic testing, when feasible. Subjects may be enrolled based on a biopsy only when a "packed marrow" precludes aspiration at the decision of the medical monitor. Results of assessments performed under SOC before the signing of informed consent may be used as the baseline disease assessment in lieu of a study-specific procedure if performed within 60 days of the first dose of study drug (Cycle 1 Day 1) and if adequate archive material is available and there has been no anticancer therapy in the interim.

Reference Section 7.9.1 for more information on tissue collection.

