7.6.4. AML, [REDACTED]: Peripheral Blood Myeloid Blast Percentage

For disease assessment timepoints in AML, [REDACTED] that do not correspond to a bone marrow examination, peripheral blood myeloid blast percentage will be evaluated by microscopic evaluation or other appropriate methodology and will be used as appropriate in conjunction with other parameters (eg, cytopenias) in determining disease status.

7.6.5. [REDACTED] AML [REDACTED]: Immunophenotyping

For subjects with relevant hematologic malignancies (eg, [REDACTED] AML [REDACTED]), immunophenotyping appropriate to the underlying pathology will be conducted by flow cytometry at the local laboratory at screening and at subsequent times only as part of confirmation of CR. Results of flow cytometry performed under SOC before the signing of informed consent may be used as the baseline disease assessment in lieu of a study-specific procedure. See Section 7.6.3 for the timing and requirements of using the preconsent SOC tissue analysis as the study baseline assessment. Results will be captured in the eCRF.

[REDACTED]

[figure not shown]
[REDACTED]

[REDACTED]

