APPENDIX D. INTERNATIONAL WORKING GROUP RESPONSE CRITERIA FOR ACUTE MYELOID LEUKEMIA

Response Category	Response Definition
Complete remission (CR) ¹	Bone marrow blasts < 5 percent; absence of blasts with Auer rods; absence of extramedullary disease; absolute neutrophil count > 1.0 × 10 ⁹ /L (1000/μL); platelet count > 100 × 10 ⁹ /L (100,000/μL); independence of red cell transfusions
CR with incomplete recovery (CRi)	All CR criteria except for residual neutropenia (< 1.0 × 10 ⁹ /L [1000/μL]) or thrombocytopenia (< 100 × 10 ⁹ /L [100,000/μL])
Morphologic leukemia-free state	Bone marrow blasts < 5 percent; absence of blasts with Auer rods; absence of extramedullary disease; no hematologic recovery required
Partial remission (PR)	All hematologic criteria of CR; decrease of bone marrow blast percentage to 5 to 25 percent; and decrease of pretreatment bone marrow blast percentage by at least 50 percent
Cytogenetic CR (CRC)	Reversion to a normal karyotype at the time of morphologic CR (or CRi) in cases with an abnormal karyotype at the time of diagnosis; based on the evaluation of 20 metaphase cells from bone marrow
Molecular CR (CRm)	No standard definition; depends on molecular target
Treatment failure	
Resistant disease (RD)	Failure to achieve CR or CRi or PR (Phase 1 trials); only includes patients surviving ≥ 7 days following completion of initial treatment, with evidence of persistent leukemia by blood and/or bone marrow examination
Death in aplasia	Deaths occurring ≥ 7 days following completion of initial treatment while cytopenic; with an aplastic or hypoplastic bone marrow obtained within 7 days of death, without evidence of persistent leukemia
Death from indeterminate cause	Deaths occurring before completion of therapy, or < 7 days following its completion; or deaths occurring ≥ 7 days following completion of initial therapy with no blasts in the blood, but no bone marrow examination available
Relapse ²	Bone marrow blasts ≥ 5 percent; or reappearance of blasts in the blood; or development of extramedullary disease

[figure not shown]

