7.4.1.2.2. Cytogenetic Response

[figure not shown]
Cytogenetic response is applicable for subjects with abnormal karyotype at baseline. Best overall response for cytogenetic response is the best response recorded before and including the time when the first event of treatment failure, relapse, or progressive disease based on altering the natural history of the disease occurs, in the order of CCyR, PCyR, no response, and NA.

BOR for cytogenetic response will be summarized descriptively. Subjects with abnormal karyotype at baseline will be included in the denominators in the summary of BOR.

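### The AML schedule footnotes waive cytogenetic testing unless CR is present, so a CRi responder can go untested yet stay in the denominator of the cytogenetic best-response summary

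*Protocol*

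**What the plan says.** **General rule.** Protocol section 7.6.3: "All bone marrow examinations should include a unilateral aspiration and biopsy with FISH and cytogenetic testing, when feasible". The same section refers the reader to the schedule-table footnotes in section 6 for the marrow requirements specific to each combination cohort.

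**Cohort rule.** Table 9 footnote i (I-DAC), Table 12 footnote j (azacitidine) and Table 18 footnote i (L-DAC) carry the same waiver: "cytogenetic testing is not required if CR is not presented".

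**Response criteria.** Protocol Appendix D, repeated in SAP Appendix B, lists CR and CRi as separate categories. CRi is "All CR criteria except for residual neutropenia" or thrombocytopenia. Cytogenetic CR is "Reversion to a normal karyotype at the time of morphologic CR (or CRi) in cases with an abnormal karyotype at the time of diagnosis".

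**Endpoint.** Protocol section 2.2.1 and SAP section 2.3.1 count CR and CRi alike in the Part 4 ORR.

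**Analysis.** SAP section 7.4.1.1 records cytogenetic status at each response visit and has separate codes for no response and for NA, which the SAP abbreviation list defines as not assessed. SAP section 7.4.1.2.2 ranks the best cytogenetic response as CCyR, PCyR, no response, NA, and adds: "Subjects with abnormal karyotype at baseline will be included in the denominators in the summary of BOR".

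**The concern.** The testing rule is narrower than the definition that it serves. The response criteria allow a cytogenetic CR to be reached at CRi, but the footnotes require the test only at CR. Whether a result exists then depends on the type of remission, which is itself an outcome. A subject in CRi whose karyotype has returned to normal, but who was not tested, cannot be placed in the CCyR row and still adds one to the denominator. Such a gap can only lower the proportion shown as cytogenetic responders. What is at stake is a descriptive summary of the depth of remission in the AML combination cohorts.

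**Working it through.** **1. Which rule a site would follow.** Section 7.6.3 is worded as an expectation, qualified by feasibility, and hands cohort detail to the footnotes. A site can reasonably treat the footnote as controlling. The waiver names only CR. Appendix D keeps CR and CRi apart, and footnote c of Table 9 itself names CR and CRp side by side. Read literally, then, testing is not required at CRi.

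**2. One subject traced through.** Take a subject on azacitidine with an abnormal baseline karyotype whose response marrow meets every CR criterion except platelet recovery.
- Appendix D: CRi.
- Primary ORR: responder.
- Table 12 footnote j: CR is not present, so cytogenetics is not required.
- If no test is done at this or any other marrow up to the first event, the SAP section 7.4.1.2.2 best response is NA.
- Denominator: included, because the baseline karyotype is abnormal.

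**3. Size.** The plan states no figure for this point, so the scale comes from the comparator rates that the protocol cites.

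Inputs: I-DAC CR 16%, CR/CRp/CRi 19% (Protocol section 1.3.1; CRp meets the Appendix D definition of CRi). Azacitidine CR 19.5%, CR/CRi 27.8% (section 1.3.2). Full cohort 43, target ORR 40% (Table 23). The documents give no separate rates for L-DAC, so that optional cohort is not sized.

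Share of remissions short of CR = (all remissions − CR) / all remissions:
- I-DAC: (19 − 16) / 19 = 0.158
- Azacitidine: (27.8 − 19.5) / 27.8 = 0.299

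Responders at target: 43 × 0.40 = 17.2. Of these, short of CR:
- I-DAC: 17.2 × 0.158 = 2.7
- Azacitidine: 17.2 × 0.299 = 5.1

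Only subjects with an abnormal baseline karyotype enter the summary. That share is not in the documents; I assume 25% to 75%:

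| Cohort | 25% | 50% | 75% |
|---|---|---|---|
| I-DAC | 0.7 | 1.4 | 2.0 |
| Azacitidine | 1.3 | 2.6 | 3.9 |

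At the smallest count that passes the final rule (13 responders), the numbers short of CR are 13 × 0.158 = 2.1 and 13 × 0.299 = 3.9 before the karyotype restriction. In a cohort stopped at Stage 1 with 3 responders they are 3 × 0.158 = 0.5 and 3 × 0.299 = 0.9.

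**4. Largest effect on the summary.** If the abnormal share is the same in these responders as in the whole cohort, it cancels. The exposed fraction of the denominator is then 0.40 × 0.158 = 6.3% (I-DAC) and 0.40 × 0.299 = 11.9% (azacitidine). The CCyR percentage would fall by that much only if every such subject went untested and every one had in fact reverted.

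**5. The Simon design.** Exact binomial sums for 3 of 13 and 12 of 43 reproduce the stated early-termination probabilities, 0.7473 at 20% and 0.1686 at 40%, with type I error 0.0496 and power 0.800. No cytogenetic result enters these rules.

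**The case against.** The case on the other side is substantial, and most of it stands as a limit on the point.

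- **Not a flat contradiction.** Section 7.6.3 is softly worded and defers to the footnotes, so the texts can be read as a general rule and its specific terms. That is fair, but under that reading testing at CRi is still not required.
- **Sites may test anyway.** A reader might infer that sites will test only CR subjects and that the summary is biased by design. The documents do not support this: the footnotes waive a requirement and forbid nothing, and section 7.6.3 still encourages the test. A subject who later moves from CRi to CR would also fall under the requirement then.
- **The primary endpoint.** A reader might infer that the CRi part of the ORR is unsound without cytogenetics. Appendix D defines CR and CRi by marrow blasts, Auer rods, extramedullary disease, counts and transfusion independence; neither needs a karyotype. The SAP's wider responder list in section 7.4.1.2.1 also includes CRi, so that difference does not bear on this point.
- **Comparison between cohorts.** The exposed share may differ by regimen, but section 4.2 plans no comparisons between subjects and section 9.5 treats the cohorts independently.
- **Display.** A reader might think untested subjects are merged with non-responders. They are not; NA has its own category.
- **Flow cytometry.** Section 7.6.5 limits on-study immunophenotyping to screening and "at subsequent times only as part of confirmation of CR". Appendix D says only that flow might assist in telling residual leukemia from recovering marrow, so extending it to CRi is a matter of choice.
- **Redaction.** Parts of sections 7.6 and 7.9 and the monotherapy schedule are blacked out, so nothing can be said about other supporting tests or about Table 6.

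**Conclusion.** The point holds as a mismatch between the three footnotes and the trial's own definition of cytogenetic CR. It affects only the descriptive best cytogenetic response summary, for which the visible SAP text defines no responder rate, interval or test. At target ORR in a full cohort, about 3 (I-DAC) to 5 (azacitidine) responders would be in remission without CR, and about 0.7 to 3.9 of them would be in the cytogenetic denominator. These are counts of subjects for whom testing is not required, not forecasts of missing results. They rest on the cited comparator rates carrying over to the combinations, on the 25% to 75% karyotype range, which is my assumption, and on enrollment reaching 43. A cohort stopped at Stage 1 would have less than one such subject on average. The ORR count, the Simon thresholds and the go/no-go decision do not change.

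**What to change.** Amend footnote i of Table 9, footnote j of Table 12 and footnote i of Table 18 so that, for subjects with an abnormal baseline karyotype, cytogenetic testing is waived only when neither CR nor CRi is present. That brings the footnotes into line with Appendix D and with the intent of section 7.6.3.

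The cost is a wording change in three footnotes and a few local cytogenetic tests on marrow that has already been drawn; no additional biopsy is needed. The SAP needs no change for this point. Extending immunophenotyping in section 7.6.5 and the schedule rows to CRi is optional.

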7.6.4. AML, [REDACTED]: Peripheral Blood Myeloid Blast Percentage

For disease assessment timepoints in AML, [REDACTED] that do not correspond to a bone marrow examination, peripheral blood myeloid blast percentage will be evaluated by microscopic evaluation or other appropriate methodology and will be used as appropriate in conjunction with other parameters (eg, cytopenias) in determining disease status.

7.6.5. [REDACTED] AML [REDACTED]: Immunophenotyping

For subjects with relevant hematologic malignancies (eg, [REDACTED] AML [REDACTED]), immunophenotyping appropriate to the underlying pathology will be conducted by flow cytometry at the local laboratory at screening and at subsequent times only as part of confirmation of CR. Results of flow cytometry performed under SOC before the signing of informed consent may be used as the baseline disease assessment in lieu of a study-specific procedure. See Section 7.6.3 for the timing and requirements of using the preconsent SOC tissue analysis as the study baseline assessment. Results will be captured in the eCRF.

[REDACTED]

[figure not shown]
[REDACTED]

[REDACTED]

7.7. Performance and Quality-of-Life Assessments

7.7.1. Eastern Cooperative Oncology Group

Performance status will be assessed on all subjects using the ECOG performance status scale ([Appendix C](#)), according to the study schedule ([Table 6](#), [Table 9](#), [Table 12](#), [Table 15](#), and [Table 18](#)).

CONFIDENTIAL

CONFIDENTIAL

7.8. Pharmacokinetic Assessments

7.8.1. Blood Sample Collection

Pharmacokinetic samples will be obtained at the visits indicated in the respective tables of PK, PD, and ECG assessments (see [Table 8](#), [Table 11](#), [Table 14](#), [Table 17](#), and [Table 20](#)) to evaluate plasma PK parameters as described in [Appendix B](#). The study drug(s) will be administered in clinic with approximately 240 mL of water. Subjects should remain fasting from food or water for at least 1 hour postdose, after which a meal or snack may be consumed. For PK sample collection, the following will be recorded:

- The exact date and time of the blood sample.
- The date and time of the last dose of study drug before blood collection (if applicable).
- The date, time, and type of the most recent meal.

Subjects will receive reminder cards in advance of the study visit providing instructions to prepare for the visit (see [Section 7.10.2](#)). Instructions for plasma preparation and sample shipping will be provided in the Laboratory Manual. The specified postdose timepoints may be adjusted based on emerging PK data.

7.8.2. Urine Sample Collection

Urine will be collected from each subject in a monotherapy cohort at Cycle 1 Day 8 after administration of INCB053914 and a predose void. Total urine will be collected over an 8-hour interval following study drug administration. Urine containers should be kept at reduced temperature (refrigerated or ice bath) during collection. After the interval, the total urine volume and the pH should be measured and recorded in the individual eCRF. Urine will be mixed thoroughly, and a 200 mL aliquot will be collected into a prelabeled, polypropylene storage bottle and frozen at or below -20°C. Shipping and handling instructions will be provided in the Laboratory Manual; samples will be analyzed by the sponsor or its designee for parameters described in [Appendix B](#).

7.8.3. Bioanalytical Methodology and Analysis

Plasma samples will be analyzed by the sponsor, or designee, using a validated assay. Additionally, residual samples may be used for exploratory analyses to identify metabolites. Pharmacokinetic parameters that will be analyzed are shown in [Appendix B](#), and the analysis methodology is described in [Section 9.4.4.5](#).

7.8.4. Food-Effect Pharmacokinetic Testing

Pharmacokinetic testing for food effect on drug exposure will be performed in at least 12 and up to 18 subjects enrolled in all monotherapy expansion cohorts who are able to participate in the food study. Subjects may be excused from the food-effect portion of the study if they are unable to consume the meal.

Subjects will have been fasted from food (not including water) overnight for at least 8 hours. A standardized high-fat, high-calorie breakfast will be given to these subjects approximately

CONFIDENTIAL

CONFIDENTIAL

30 minutes before administration of study drug. Subjects must consume the entire breakfast within 25 minutes, and study drug administration will begin 5 minutes after completing breakfast.

The high-fat, high-calorie breakfast (50% kcal from fat) will consist of:

- 2 eggs fried in butter
- 2 strips of bacon
- 1 English muffin with butter
- 4 oz hash brown potatoes
- 8 oz whole milk

Alternative menus with the same caloric and fat content may be substituted with the prior approval of the study sponsor.

7.9. Pharmacodynamic and Biomarker Assessments

[REDACTED]

CONFIDENTIAL

CONFIDENTIAL

7.9.2. Buccal Swab

A buccal swab will be performed at screening on all subjects as a source of nontumor genetic material. Details of collection and shipping will be provided in the Laboratory Manual.

[REDACTED]

7.9.4. Whole Blood Pharmacodynamics (Monotherapy Cohorts Only)

Whole blood PD samples will be generally collected in conjunction with the timed PK samples (see [Table 7](#) and [Table 8](#)) for the measurement of drug effect (phosphoprotein analysis in whole blood). These samples must be shipped directly (unfrozen) to the sponsor, **on the day of collection**, for processing and analysis. Refer to the Laboratory Manual for detailed collection, handling, and shipping instructions.

[REDACTED]

[REDACTED]

[REDACTED]

[REDACTED]

[REDACTED]

7.10. Other Study Procedures

7.10.1. Administration of Study Drug in the Clinic

Study drug will be administered in the study clinic on days when it is necessary to collect a trough (predose) sample and when timed post-dose samples are collected.

